VibeTech One, a semi-recumbent strength training and vibration therapy system (VibeTech, Inc., Sheboygan, WI), while performing leg presses against the system's vibrating footplate. The footplate supplies low-level vibrations comfortably from the feet through the legs and into the low back at 30 Hz. This frequency is commonly reported in the vibration therapy literature in association with a variety of musculoskeletal benefits. Moreover, vibrations supplied to the legs near this frequency induce the tonic vibration reflex (TVR), which results in the affected muscles contracting in a controlled, but involuntary manner when the muscles are stimulated with appropriately delivered vibration. The vibration supplied through the footplate is considered safe according to ISO2631 (ISO2631-1:1997). The vibration amplitude produced by the VibeTech One has an adjustable range from 0.05 to 0.5 mm. The higher the vibration amplitude, the higher the alternating force supplied to the muscle at 30 Hz. For example, a vibration amplitude of 0.05 mm peak-to-peak produces an alternating force of +/-4 lbs. A vibration amplitude of 0.5 mm peak-to-peak produces an alternating force of +/-22 lbs. This alternating load is absorbed by the muscles, tendons, ligaments, bones, cartilage, and other tissues of the affected region. While it is not known how much vibration reaches each tissue, it is hypothesized that larger amplitude vibrations result in a larger amount of force being absorbed by the muscles through the TVR. In clinical use with the VibeTech One (where over 400 treatments have been supplied to nursing home residents to date), therapists typically apply a larger vibration amplitude when a higher leg pressure is selected. As such, vibration amplitude and leg pressure will increase in a linear fashion as patients progress in this study.

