The footplate is force driven with a robotic loading mechanism that supplies between 5 and 100 lbs of force to the user's legs depending on the ability level of the participant. This force is increased as tolerated by the user. Clinical use of the equipment has shown that an initial force on the order of 40 lbs is appropriate for most nursing home therapy patients, while specific conditions may warrant a lower starting force (e.g., 25 lbs has worked well as a starting load for knee replacement patients according to therapy staff using the equipment). The therapist carefully monitors patient progress and increases the force in 5 lbs increments over the course of treatment as the patient progresses. The same approach will be used in this study by our training supervisors.

The footplate moves slowly, taking between 20 and 30 seconds to complete one leg press depending on the range of motion of the participant. This encourages the participant to apply slow and controlled pressure while vibrations are transmitted through the major muscle groups of the legs (quads and hamstrings) while the muscles traverse throughout their physiological range of motion (0-90 degree knee flexion). If a participant wishes to take a break, they are allowed to hold their legs in a fixed position while the load is maintained. If a participant becomes fatigued during treatment, the therapist will stop treatment and record the length of the session endured. Treatment sessions are prescribed to be 10-minutes in duration, and will be applied as often as deemed fit by the therapy staff (the target is 3x per week).

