The VibeTech One Rehab Chair allows vibration exercise while being semi-recumbent. This is a major advantage for older adults with co-morbidities as fear of falling, fatigue, chronic pain or cardio/respiratory disease in older adults thus preventing them from standing vibration exercise. The VibeTech One Rehab Chair is configured to allow users to receive vibration training to their legs while seated, removing concerns of balance and fear of falling and does not require substantial cardio/respiratory effort. The applied load simulates the weight of standing (or partial bodyweight) by applying a force on a footplate, while restraining movement of the knees and back. This design requires no effort from the user, which makes it accessible to people who are too weak or otherwise unable to use standing vibrating platforms or participate in traditional exercise. Participants will be asked to train for 10 minutes 3 days per week. In the "loading + vibration group" (intervention group) vibratory acceleration will be 30Hz and the applied load will be 50% of body weight up to a device maximum applied load of 100 lbs. Vibration intensity will initially be set to 0.2 g and will increase by 0.2 g every other week, as tolerated by the participant, and max out at 1.0 g. In the "loading only" group (control group) participants will be seating in the vibration device and will experience loading of their leg muscles through the device. Participants will be screened

for discomfort during every treatment. If an increase in vibration intensity causes any discomfort, that participant will maintain the same vibration exercise dosing as the prior 2 weeks.

During training sessions participants will be able to stop exercising whenever they chose to. They will be encouraged to continue their training session after a short break to finish 10 minutes of exercise, but if they decline the session will be ended. The participant will be asked why they stopped and these comments will be recorded. After that an appointment for the next session will be offered.

SPPB

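### The plan's leg-load rules conflict, and no sentence requires equal load in the vibration and loading-only conditions, so a load difference could be mixed into the vibration effect

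*Combined protocol and SAP*

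**What the plan says.** Under Study Procedures, each participant has one eight-week period of vibration plus loading and one of loading only, which the protocol calls sham, separated by a four-week washout. The Vibration Training section then deals with load in three places.

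- **First paragraph.** After noting that therapists tend to pair larger amplitudes with higher leg pressures, it states that "vibration amplitude and leg pressure will increase in a linear fashion as patients progress in this study".
- **Second paragraph.** Force depends on the user's ability. From clinical use, "an initial force on the order of 40 lbs is appropriate for most nursing home therapy patients", with less for some conditions. The therapist then "increases the force in 5 lbs increments over the course of treatment as the patient progresses". The paragraph ends: "The same approach will be used in this study by our training supervisors". No group is named.
- **Fourth paragraph.** In the sentence on the vibration group, "the applied load will be 50% of body weight up to a device maximum applied load of 100 lbs". The sentence on the control group says only that "participants will be seating in the vibration device and will experience loading of their leg muscles through the device".

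On movement, the third paragraph describes a slow leg press of 20 to 30 seconds without naming a group, then says that this leads the participant to "apply slow and controlled pressure while vibrations are transmitted through the major muscle groups of the legs". The Treatment part of the Safety section has the treatment supervisor operate the device.

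**The concern.** The contrast of interest is vibration versus no vibration on top of the same leg loading. Loading is itself an exercise dose: the protocol describes the device as a strength-training as well as a vibration system. If load differed between conditions, the within-person difference in jump power would reflect both vibration and load. Changing over from one condition to the other would not repair this, because the load difference would move with the treatment.

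The plan gives more than one rule for the load. One is attached to the vibration group only, and another refers to amplitude, which only that condition has. Where the rules leave a choice, it falls to the training supervisor. This appears to be the same role that operates the device, and so knows whether vibration is on.

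**Working it through.** **Step 1. The rules side by side (all from Vibration Training).**

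| Paragraph | Load | Change over time | Condition covered |
|---|---|---|---|
| First | not given | rises along with amplitude | vibration; unclear for loading only |
| Second | by ability, about 40 lbs in clinical use | 5 lb steps, at the supervisor's judgement | no group named |
| Fourth | 50% of body weight, maximum 100 lbs | none stated | vibration group only |

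These cannot all hold for the vibration condition. Vibration intensity starts at 0.2 g and rises by 0.2 g every other week, as tolerated. At a fixed 30 Hz, amplitude rises with it. The first paragraph then has leg pressure rising too, whereas half of a stable body weight stays constant. A load that starts by ability and climbs in steps is different again.

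**Step 2. How far apart the rules could be.** The documents give no body weights and no step frequency, so both are assumptions. The 40 lb start describes nursing home therapy patients, whereas the trial enrols community-dwelling adults; it is used here only as the plan's own example.

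Fixed-share rule, for assumed weights of 120, 160 and 200 lbs: 0.5 × 120 = 60, 0.5 × 160 = 80, 0.5 × 200 = 100 lbs.

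Stepwise rule from 40 lbs, over 8 weeks × 3 = 24 sessions:

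- A step every two weeks: 40, 45, 50, 55; mean 47.5 lbs.
- A step every week: 40 up to 75; mean (40 + 75)/2 = 57.5 lbs.
- A step every session: 40 up to 95 over 12 sessions (mean 67.5), then 100 for 12 sessions; mean (67.5 + 100)/2 = 83.75 lbs.

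Stepwise relative to fixed share:

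| Stepwise load | vs 60 lbs | vs 80 lbs | vs 100 lbs |
|---|---|---|---|
| Session 1 (40) | −33% | −50% | −60% |
| Mean 47.5 | −21% | −41% | −52.5% |
| Mean 57.5 | −4% | −28% | −42.5% |
| Mean 83.75 | +40% | +5% | −16% |

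The rules are not interchangeable, and the sign of the gap depends on how fast the supervisor steps up.

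**Step 3. Why the crossover does not remove a load difference.** Let τ be the vibration effect, π the period effect, ΔL the load in the vibration condition minus the load in loading only, and λ the effect of load on jump power. The expected difference, period 1 minus period 2, is:

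- vibration first: π + (τ + λΔL)
- loading only first: π − (τ + λΔL)

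Half the difference between the sequences is τ + λΔL. The period effect cancels; λΔL does not. The documents give no value for λ, and ΔL depends on which rule is followed, so λΔL cannot be calculated.

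**Step 4. What ΔL would be under each reading.**

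- Half of body weight in both conditions: ΔL = 0, but the text does not prescribe this for loading only.
- Stepwise in both: ΔL = 0 only if progression happens to match. Steps follow patient progress and tolerance, so if vibration affects either, the loads diverge.
- Titration towards half of body weight in both: ΔL depends on the pace in each condition.
- Half of body weight with vibration, stepwise without: ΔL is the gap in Step 2.

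Only the first reading guarantees equality. The sample size does not enter this argument.

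**The case against.** The best defence is that matched loading was plainly intended. The conditions are labelled vibration plus loading and loading only, the same people use the same device, and session length and frequency are set in common for all participants. The second paragraph's load rule and the third paragraph's leg press name no group and can be read as covering both conditions. The first paragraph might mean only that both quantities rise steadily over time. All of this is fair, and it rules out several stronger readings.

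- A reader might infer that the control has no load or footplate movement stated at all. The text does not support that. What is missing is an amount in the control sentence and a statement that the leg press is the same in both conditions.
- A reader might infer that a supervisor following the text would give half of body weight with vibration and a discretionary load without. That is one reading of several; the stepwise rule, naming no group, applies just as well to the vibration period.
- A reader might infer a particular bias or error rate. No effect of load on jump power is given, so none can be derived.
- A reader might infer that load will go unrecorded. The protocol mentions recording session length when a participant tires, reasons for stopping and adverse events, and does not name load, but the session forms are not in the document.

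What survives is that intent is not a rule. On the most favourable group-neutral reading, load is still left to judgement and still contradicts the fixed share.

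**Conclusion.** The point holds as a conflict between written rules together with a missing requirement of equal load. A load difference could enter the within-person vibration effect without being removed by the crossover. Its size and direction cannot be determined: the load figures above rest on assumed body weights, an assumed step frequency and a starting load taken from a different population, and they show only that the rules diverge. The documents do not show that loads would in fact differ, or that the primary result would be biased. That the person setting the load knows the condition is an inference from the supervisor's two described tasks. For a pilot with a wording-level remedy, this is worth correcting but is not a fundamental flaw.

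**What to change.** - State one load rule, with starting load, cap and progression, and apply it to both conditions and both periods. Repeating each participant's period 1 loads session by session in period 2 is one option, subject to tolerance.
- State that loading only uses the same leg press, range and instructions with vibration off. Reconcile this with the device description, which has the load applied "by applying a force on a footplate, while restraining movement of the knees and back".
- Delete whichever of the fixed-share and 5 lb rules is not used, and delete the first paragraph's link between amplitude and leg pressure.
- Record applied load at every session and report it by condition.

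The cost is protocol and training-instruction wording and, if it is not already there, one field on the session log. No visits, staff or participants are added. The change does not address the supervisor's awareness of vibration, but it leaves less for that awareness to influence.

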Exploratory Aim/Hypothesis:

Exploratory Aim: Examine adherence and factors that influence adherence, specifically subjective health benefit, exercise enjoyment (5-point Likert scales), pain (Comprehensive Pain Assessment Form), exercise related self-efficacy (Self-Efficacy for Exercise Scale), mood (Geriatric depression scale), and social support network (Lubben Social Network Scale). Our hypothesis is that vibration exercise will be well liked, not cause pain, and found to be beneficial by participants. Further more adherence will be influenced by parameters such as mood, social support network and exercise self-efficacy.

Background:

Sarcopenia: Definition, Prevalence and Consequence

With advancing age, a decrease in muscle function and mass occurs; a phenomenon known as sarcopenia. Although sarcopenia definitions have been proposed, no single consensus definition exists. As such, it is not surprising that studies evaluating sarcopenia prevalence and consequences have used different methodologies to evaluate muscle mass and/or to quantitate function. Despite variable definitions, it is apparent that sarcopenia becomes common with advancing age. Our own data in a small sample of community dwelling older adults demonstrated this variation in sarcopenia prevalence (from 11 to 34%) depending which definition was used. In a much larger cohort (NHANES III) sarcopenia prevalence was estimated to be 7-11% in older adults. Using definitions that include muscle mass and function the prevalence tends to be higher, particularly in older populations. Sarcopenia is associated with increased disability and reduced ability to perform activities of daily living, increased risk of falls and fractures, increased morbidity/mortality and is associated with substantial healthcare costs estimated at \$18.5 billion annually. In summary, sarcopenia is common, costly and associated with adverse health consequences. It is apparent that clinical recognition of sarcopenia and therapies to prevent or correct this common condition, will have major societal and personal benefit including reduction of falls/fractures and loss of independence.

Vibration

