Medical history	X									
Hand grip strength		X		X		X		X		
Jumping mechanography		X		X		X		X		
BIS		X		X		X		X		
Timed Up and Go (TUG)		X		X		X		X		
SPPB	X	X		X		X		X		
AM-PAC questionnaire		X		X		X		X		
Comprehensive Pain Assessment Form		X		X		X		X		
Geriatric Depression Scale		X		X		X		X		
Self-Efficacy for Exercise Scale		X		X		X		X		
Lubben Social Network Scale		X		X				X		
Physical Activity Scale for the Elderly		X		X		X		X		
Falls Assessment			Will be done on a weekly basis							
Adverse event recording and safety survey			Will be done at every training session							

Study Procedures

The study consists of five visits; screening, baseline followed by eight weeks of training three times a week, visit 1 at eight weeks followed by 4 weeks of washout, Visit 2 at 12 weeks followed by eight weeks of training three times a week, and a final Visit 3 at 20 weeks.

The following will occur at the screening visit after obtaining consent. Volunteers will be asked to perform tests included in the SPPB (gait speed, chair rise, balance). If their score is ≤ 9 or ≤ 2 in any of the three tests included in the SPPB they will be eligible for the intervention phase. Included participants will be asked information about their medical history including personal history of osteoporosis, fragility fractures and falls within the last 12

months. At the baseline visit several questionnaires will be obtained and participants then will proceed with muscle function tests (SPPB, jumping mechanography, grip strength, timed-up-and-go test).

Participants will then be randomized into one of two groups. The first group will receive vibration + loading treatment for the first 8 weeks, the second group will receive sham treatment (loading only). After 8 weeks both groups will go through a 4 week wash-out period and then crossover will occur. The first group will now receive sham treatment (loading only) while the second group will receive vibration + loading treatment. The participants will train for 10 minutes, 3 times a week, during the active 16 total weeks.

Vibration Training

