The information collected from the participants will be handled confidentially to the extent provided by the law. The participants' information will be assigned a code number and identified by their initials. The list connecting their name to these identifiers will be kept in a locked file. Only researchers directly involved with the project will have access to the list. Participant names will not be used in any report. At the conclusion of the study, participants will be asked if they would like to have their treatment charts transferred to their designated medical professional. Data transferred to designated medical professionals will be handled confidentially to the extent provided by the law.

Data generated for this study will be managed by [name] staff. UW data managers will enter data 100% twice, independent of the initial entry, preferably by a different individual. Should it be necessary to have the same individual enter data, at least seven days will transpire between entry cycles. Any discrepancy between entries will be verified and corrected.

Statistical Analysis

ICTR biostatisticians will do the randomization and subsequent data analysis of the primary and exploratory aims, in concert with the study investigators and consultants. Repeated measures ANOVA will be used to test the primary hypothesis. Descriptive analyses and correlation analyses and regression models will be used to test the exploratory aim.

Power Analysis

Sample size estimation was conducted based on the primary outcome variable of weight corrected jump power. To detect a 10% difference in maximum jump power between control and intervention groups, 26 subjects are needed per group (alpha=0.05; 80% power; 2-sided) assuming a standard deviation of 2.6 and control group mean of 21 W/kg. These values are based on data previously collected by our group involving 81 older adults. Accounting for up to 20% subject withdrawal brings the required enrollment to 32 subjects per group (64 total). Due to budgetary constraints we are proposing a simple AB/BA crossover design (i.e. participants treated with the intervention also serve as the control group, and a washout period is provided to ensure that no training effects exist between the treatment and control periods) to reduce the number of needed participants to 32 patients."

Adverse Experience Reporting

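### The protocol does not say whether participants who stop training are still measured at Visits 1 to 3, so the jump-power estimate could rest on completers, and pain forms after vibration could be missing

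*Combined protocol and SAP*

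**What the plan says.** All references are to the combined protocol and SAP.

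- **Allowance for leaving (Power Analysis).** The only provision is a larger enrolment: "Accounting for up to 20% subject withdrawal brings the required enrollment to 32 subjects per group (64 total". It was worked out for two parallel groups. A crossover is then adopted "to reduce the number of needed participants to 32 patients".
- **Visits (Study Procedures, Study Flow Chart).** Visits follow the calendar: "visit 1 at eight weeks followed by 4 weeks of washout, Visit 2 at 12 weeks", with Visit 3 at week 20. Jumping mechanography and the Comprehensive Pain Assessment Form are scheduled at baseline and at Visits 1, 2 and 3. No minimum training attendance is attached to a visit.
- **Stopping a session (Vibration Training; Potential Risks, Treatment).** Breaks are allowed, the session length or the reason for stopping is recorded, the next appointment is offered, and discomfort is screened at every treatment. Giving up training altogether is not addressed.
- **Partial participation (Psychological Risks).** Volunteers may refuse any part of the study. The text does not say whether their visits then continue.
- **Analysis (Statistical Analysis).** The primary test is a repeated measures ANOVA. The exploratory aim uses descriptive summaries, correlations and regression. There is no analysis set, missing-data method or rule for people with one period only.
- **Pain hypothesis (Exploratory Aim/Hypothesis).** The expectation is that "vibration exercise will be well liked, not cause pain, and found to be beneficial by participants".

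**The concern.** Stopping training and leaving the study are different events, and the protocol treats neither explicitly. The assessments fall at fixed weeks and do not need training to have continued, so they could be obtained from someone who has stopped. Without an instruction, staff must decide case by case, and a visit value that was never taken cannot be recovered in the analysis.

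Stopping could plausibly differ between conditions. Only the vibration condition has an intensity that is stepped up every other week, with a rule for discomfort, and delayed muscle soreness is described for vibration therapy. If people who do poorly on vibration are the ones not measured, the primary comparison would look better than it is. With 32 participants, a few such losses matter. Adherence and what influences it are also an exploratory aim, and those who stop are the most informative people for it.

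**Working it through.** **1. The plan's own figures.** Inputs from Power Analysis: "To detect a 10% difference in maximum jump power between control and intervention groups, 26 subjects are needed per group", "assuming a standard deviation of 2.6 and control group mean of 21 W/kg", "alpha=0.05; 80% power; 2-sided".

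- Difference: 0.10 × 21 = 2.1 W/kg.
- Normal approximation: 2 × [2.6 × (1.960 + 0.842) / 2.1]² = 24.06, so 25 per group.
- Two-sample t-test: 25.06, so 26 per group. This matches the plan; power at 26 per group is 81.5%.
- Withdrawal: 26 × 1.2 = 31.2, so 32 (the plan's figure). Dividing instead, 26 / 0.8 = 32.5, so 33. The difference is immaterial here.
- In the crossover, 32 × 0.8 = 25.6, so about 26 completers and 6 who leave (6/32 = 18.75%).

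**2. Which values are lost if a person stops and is not measured again.**

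| Sequence | Stops in | Vibration value | Sham value |
|---|---|---|---|
| Vibration first | Period 1 (vibration) | lost | lost |
| Vibration first | Period 2 (sham) | kept | lost |
| Sham first | Period 1 (sham) | lost | lost |
| Sham first | Period 2 (vibration) | lost | kept |

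A complete-case analysis drops all four. The pattern itself favours neither condition. Bias arises only if those who stop would have responded differently from those who stay.

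**3. Size of the bias in jump power.** Let p be the share who stop, Dc the vibration-minus-sham effect in completers and Dq the effect that those who stop would have shown at the scheduled visits.

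Effect in all randomised = (1 − p) × Dc + p × Dq, so the completers' excess is p × (Dc − Dq).

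With p = 6/32 and Dc = 2.1 W/kg (the planned effect), and Dq assumed:

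| Dq (W/kg) | All randomised (W/kg) | Completers / all |
|---|---|---|
| 2.1 (same gain) | 2.10 | 1.00 |
| 1.05 (half) | (26 × 2.1 + 6 × 1.05)/32 = 1.90 | 1.10 |
| 0 (none) | (26 × 2.1)/32 = 1.71 | 1.23 |
| −1.05 (loss of half) | (26 × 2.1 − 6 × 1.05)/32 = 1.51 | 1.39 |

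At exactly 20% loss and Dq = 0, the result is 0.8 × 2.1 = 1.68 W/kg, a factor of 1.25. If Dq exceeded 2.1, completers would understate the effect.

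**4. Power if everyone is measured.** The within-person correlation ρ is not given, so a range of 0 to 0.7 is assumed. SD of the within-person difference = 2.6 × √[2(1 − ρ)]; noncentral t with N − 2 degrees of freedom; 1:1 allocation assumed. Extra variance from mixing responders and non-responders is ignored.

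| ρ | 26 completers, 2.1 W/kg | All 32, 1.71 W/kg |
|---|---|---|
| 0 | 80% | 72% |
| 0.3 | 92% | 86% |
| 0.5 | 98% | 95% |
| 0.7 | >99% | >99% |

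**5. Pain.** Suppose the form shows no pain problem in any of 26 completers. The exact two-sided 95% upper limit is 1 − 0.025^(1/26) = 13.2%. If between none and all of the 6 others left because of pain, the rate among all 32 lies between 0% and 6/32 = 18.8% (exact 95% interval for 6/32: 7.2% to 36.4%). The completers' forms cannot tell these apart.

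**The case against.** **The plan is silent; it does not exclude anyone.** This stands. A reader might infer that people who stop training are taken off the visit schedule. Nothing says so. Visits are set by calendar week, volunteers may refuse one part of the study only, and making adherence an outcome fits better with assessing poor adherers than with discarding them. The consent pages are not in the copy reviewed, so what they say about follow-up is unknown. What remains is that the protocol does not state it.

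**The loss need not fall on vibration.** This also stands. Sham uses the same chair and leg loading, so people can stop there too. A reader might infer that the missing value is always the vibration one, but that follows only if stops during vibration alone are considered.

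**Completers-only is not specified.** Correct. The plan names a repeated measures ANOVA without its form. In its usual complete-case form it drops anyone missing a period; a mixed model would keep one-period data. Even so, a mixed model relies on an assumption about the missing values and does not replace them.

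**Pain is captured elsewhere.** Largely correct. Adverse events and a safety survey are recorded at every training session, discomfort is screened at every treatment, reasons for stopping a session are recorded, and participants are asked to report significant events between visits. A reader might infer that the pain claim would rest only on people who tolerated both conditions. The exploratory analyses do not require both periods, so a vibration-first participant who reaches Visit 1 contributes. Also, soreness is described as delayed by up to 4 days, so someone who stopped in week 3 could be pain-free at week 8. A late visit score could therefore understate pain during vibration, and following people up does not by itself settle the question.

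**Conclusion.** The gap is real and narrow. Over-enrolment is the only provision for people who leave, and the documents do not say whether those who stop training are still measured or how their data enter the analysis.

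For jump power, the estimate rests on completers if two things happen: those who stop are not measured, and the ANOVA is run on complete cases. The factor of 1.23 is an illustration that combines 6 stops out of 32 with no gain in any of them. It is not a forecast, because the documents give no stopping rates by condition. No bias at all is equally compatible with the documents.

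For pain, what is missing is the Comprehensive Pain Assessment Form after vibration in people who quit during vibration.

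The sample-size arithmetic is not in question. The case for acting is that the change is cheap and must be in place before people stop.

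**What to change.** In Study Procedures:

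- Separate stopping training from withdrawing consent for follow-up.
- Ask anyone who stops training, in either period, to attend the remaining scheduled visits (weeks 8, 12 and 20) and complete the assessments they agree to and can do. As a minimum, obtain the questionnaires by interview, which is already the planned mode.
- Record the date, period, condition and main reason for stopping.

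In Statistical Analysis:

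- Analyse all randomised participants by the condition assigned in each period, with a mixed model that includes people who have data from one period only. Add a sensitivity analysis for values still missing.
- Report pain-related stops by condition among all who started that condition, because a late visit score may miss pain that has resolved.

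Cost: protocol wording, and consent wording if it does not already cover this. No new visit or procedure is needed: the conduct site's coordinator already arranges testing visits and the lead site's staff already run them. The downsides are some effort to bring back people who no longer train and a possibly smaller estimated effect. In the illustration, power stays at 86% or more for a within-person correlation of 0.3 or higher and falls to 72% at zero correlation.
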